## **8.6 Immunogenicity assessments**

As rhAnnexin-V 128 is an exogenous protein, development of antibodies against the protein must be assessed in order to evaluate the risk and consequences of such development.

Assays for anti-rhAnnexin V-128 IgG and IgM antibodies will be performed in serum samples by ELISA at screening visit. An additional sample is required at Day 30.

For this purpose 10 mL blood samples will be collected at screening and Day 30. At each time-point, after centrifugation, serum will be divided into six aliquots and frozen (-80°C). Three out of six serum aliquots will be then shipped to the central laboratory at [REDACTED]. Remaining samples will be shipped only if required for analysis and destroyed at study end if not required. Blood Samples Handling will be detailed in the Laboratory Manual provided by [REDACTED].

## **9 DATA MONITORING COMMITTEE (DMC)**

The DMC consists of representatives of investigators and Sponsor representatives and could include external person such as independent experts, if judged appropriate by the Sponsor. The main function of the committee will be to review the images of the first 5 patients and determine if there is a premature high evidence of the presence of inadequate technical performance in this patients group. The DMC will also determine if there is a high evidence of an excess of adverse events.

The DMC will review and evaluate the images of the first 5 patients in terms of image quality visual efficacy (uptake) and clinical relevance of the study product. The DMC will also review the examinations of safety data. The DMC will promptly give recommendations to continue or terminate the study. The DMC report will be edited by the Sponsor and sent to the ethics committee as well as competent authorities.

Preliminary results can be used by the Sponsor for publication purpose, before the end of the main trial.

## **10 STATISTICAL CONSIDERATIONS**

The statistical analysis of the present study will be performed in accordance with the principles stated in the Consensus-Guideline E9 (Statistical Principles for Clinical Trials) of the International

Conference on Harmonization (ICH).

Statistical method will be described in details in the statistical analysis plan (SAP). The considered approach is summarized here after.

### **10.1 General Statistical considerations**

If not stated otherwise, all statistical analyses will be conducted as follows.

Categorical data will be presented as frequencies, percentages and 95% confidence interval if relevant. For continuous data, N, missing, mean, standard deviation, median, quartiles, minimum, maximum and if relevant 95% confidence interval will be presented. Graphs such as box plots, circular diagrams or histograms can also be computed if relevant. p-values of 0.05 or lower will be considered as statistically significant. No adjustment will be made for multiple testing and missing data will not be replaced. Considering the small sample size planned in this study, non-parametric approach will be favored.

### **10.2 Sample size**

The number of patients in this study is not based on statistical power considerations. The planned sample includes 20 patients which is the number believed to provide sufficient data to assess the potential of 99mTc-rhAnnexin V-128 to image disease severity in SpA patients and provide sufficient preliminary data to plan larger pivotal trials focusing on the confirmation of the benefit for this new imaging procedure for the early diagnosis of SpA.

At first, five patients will be recruited and analyzed as a Proof of Concept (PoC). In the PoC part of the study, medical images will be reviewed by the DMC in charge of assessing the imaging potential of 99mTc-rhAnnexin V-128 in terms of image quality, uptake and medical relevance. After reaching a consensus, the committee will decide if the clinical investigation should continue with the remaining 15 patients. The planned number of patients in the PoC study is not based on statistical considerations. However, this number of patients should provide sufficient relevant information for the evaluation of the images in terms of quality and medical relevance.

### **10.3 Demographics and Other Subject Characteristics**

Demographic and other baseline data will be summarized descriptively. All background and demographic/SpA diagnostic data will be listed in detail.

### **10.4 Concomitant Medications**

Concomitant medications (including treatments for the underline disease) will be coded using World Health Organization (WHO) dictionary. Type and incidence of concomitant medications will be tabulated (generic terms).

### **10.5 Laboratory Tests**

Descriptive statistics including shift tables will be generated for all laboratory tests performed i.e. the

actual values by cross-tabulations (with classes for below, within, and above normal range). Laboratory data will be analyzed with respect to the normal ranges of values provided by the local laboratory and abnormal laboratory test results will be tabulated.

## **10.6 Vital Signs**

The statistical analysis of vital signs measurement will be mainly descriptive in nature.

## **10.7 Physical Examination**

Physical examination findings will be listed.

## **10.8 Adverse Events**

All original AEs terms will be coded using the Medical Dictionary for Regulatory Activities (MedDRA). System organ classes and preferred terms will be used in the analyses.

Type and incidence of AEs, as well as severity and relatedness to the study medication will be tabulated. Special attention will be given to those patients who prematurely discontinue the study or the study medication due to an AE, or who experience a severe AE or an SAE.

## **10.9 Analysis of efficacy**

### **Primary endpoint:**

In order to assess 99mTc-rhAnnexin V-128 magnitude and dynamic range of uptake within areas affected by inflammation, SPECT/CT scans will be interpreted and graded by at least two independent experienced nuclear medicine physicians blinded from clinical data and other imaging modality results. Briefly, 99mTc-rhAnnexin V-128 uptake compared with background (e.g. physiological liver uptake) should be assessed for each affected area by nuclear medicine physicians using a 4-grade scoring system (e.g. 0, none; 1, mild or present but < to background uptake; 2, moderate or = to background uptake; 3, intense or > to background uptake). In case of discrepancies between the different readers, an adjudication process based on consensus should be put in place in order to obtain one final outcome for each area.

### **Secondary endpoints:**

Briefly, for quantifying the radioactivity uptake after injection of 99mTc-rhAnnexin V-128, ROIs will be drawn manually on the earliest images, and the shapes and sizes (i.e., number of pixels) will be kept constant over all subsequent images. Correction for background counts will be performed using an appropriate background region by subtracting the mean counts per pixel in the background region from the mean counts per pixel in each ROI to yield net counts. For each ROI, the geometric mean of net counts, corrected for physical decay, of total anterior and posterior counts will be calculated.

In order to compare SPECT/CT scans and MRI scans, diagnostic performances will be evaluated in terms of sensitivity (i.e., true positive rate), specificity (i.e., true negative rate), positive predictive value (i.e., proportion of positive values) and negative predictive value (i.e., proportion of negative values). To do this, physical examinations will be necessary to define sites of pain in patients with

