## 1 SYNOPSIS

Investigational Medicinal Product	Kit for the Preparation of Tc-99m Recombinant Human Annexin V-128 for Injection
Title of the study	Phase II Study of 99m Tc-rhAnnexin V-128 Radionuclide Imaging in Patients with Clinical Suspicion or Confirmed Diagnosis of Spondyloarthritis (SpA).
Clinical Center	Cedars-Sinai Medical Center [name] United States
Investigators	Dr [REDACTED], MD Dr [REDACTED], MD
Corporate Sponsor	Advanced Accelerator Applications USA, Inc.
Subject's Indication	Patients with Clinical Suspicion or Confirmed Diagnosis of Spondyloarthritis (SpA)
Objectives	
Primary Objective
 
 
- To determine the magnitude and dynamic range of 99mTc-rhAnnexin V-128 uptake in disease affected sacro-iliac or lumbar spine joints, in patients with clinical suspicion or confirmed diagnosis of Spondyloarthritis (SpA).
 
 
Secondary Objectives:
 
 
- To determine the clinical utility of 99mTc-rhAnnexin V-128 SPECT/CT imaging in the identification of chronic osteoarthritic active sites of SpA compared with conventional imaging (Magnetic Resonance Imaging), in patients with disease affected sacro-iliac, or lumbar spine joints.
 
- To assess the presence of antibodies against rhAnnexin V-128 at baseline and post-treatment
 
- To determine the localization pattern and magnitude of focal uptake of 99mTc-rhAnnexin V-128 within the abdomen in patients with clinical suspicion or confirmed diagnosis of Spondyloarthritis (SpA).
 
 

Rationale	Annexin V is an endogenous human protein that binds to phosphatidylserine (PS), a constitutive anionic phospholipid of the plasma cell membranes in all

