**Study Protocol**

and PT will be counted only once for that SOC and PT. The incidence of adverse events will also be summarized by severity.

All other safety variables will be tabulated at each measuring time together with descriptive statistics, if appropriate. Hematology, clinical chemistry, urinalysis and immunogenicity data will be analyzed. Similarly, descriptive statistics will also be provided for vital signs, physical examination, etc.

Efficacy by  $^{99m}\text{Tc}$ -rhAnnexin V-128 uptake will be assessed qualitatively and semi-quantitatively in sacro-iliac joints and in the lumbar spine of patients with clinical suspicion or confirmed diagnosis of SpA. Sensitivity and specificity of  $^{99m}\text{Tc}$ -rhAnnexin V-128 SPECT/CT imaging compared to MRI will be evaluated based on the clinical follow-up information as the standard of truth for disease diagnosis.

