**Study Protocol**

Knowledge of the expected dynamic range of the disease related changes in  $^{99m}\text{Tc}$ -rhAnnexin V-128 uptake in correlation with clinical measured of disease severity within affected joints will be critical for the power calculations and sample size estimates as part of the design of a follow up studies in SpA patients in order to further demonstrate the benefit of this new imaging procedure versus conventional imaging with MRI and plain film radiography. Furthermore, it is expected that the quantitative capabilities of SPECT/CT and the inherent sensitivity of  $^{99m}\text{Tc}$ -rhAnnexin V-128 imaging and reduced cost will replace MRI as a screening tool for the work up of patients with SpA.

As secondary goal, we also wish to determine the ability (specificity) of  $^{99m}\text{Tc}$ -rhAnnexin V-128 to distinguish between active autoimmune arthritis versus osteoarthritis particular of the lumbosacral spine and SI joints of patients with SpA. We also hypothesize that some of SpA patients with active disease have subclinical Crohn's disease. Therefore, we wish to perform a pilot study on the localization of  $^{99m}\text{Tc}$ -rhAnnexin V-128 in the abdomen.

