### **4.2 Study hypotheses**

We hypothesize that  $^{99m}\text{Tc}$ -rhAnnexin V-128; a second generation form of  $^{99m}\text{Tc}$  radiolabeled annexin V with significantly higher PS binding affinity and improved in vivo localization properties, will be highly specific in imaging degenerative osteoarthritis particularly of the lumbosacral spine

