**Study Protocol**

clinical suspicion or confirmed diagnosis of SpA. When sites of pain will match with abnormalities on diagnostic images, this will be regarded as true positive. McNemar test will be used to compare diagnostic performances of SPECT/CT and MRI techniques.

The determination of antibodies against rhAnnexin V-128 at baseline and post-treatment will be described as present or absent, and if applicable, its presence will be correlated as per the [REDACTED] objectives.

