4.1.4 Study hypotheses and justification

It is hypothesized that ^{99m}Tc-rhAnnexin V-128, a second generation form of ^{99m}Tc radiolabeled annexin V with significantly higher PS binding affinity and improved in vivo localization properties, will be highly specific in imaging degenerative osteoarthritis particularly of the lumbosacral spine and sacroiliac joints as seen by SPECT/CT in patients with SpA. It is also hypothesized that ^{99m}Tc- rhAnnexin V-128 will be localized within the abdomen of SpA patients with active disease showing suspicious Crohn's disease.

At the completion of this study, there will be preliminary data on the expected magnitude and dynamic range and specificity of ^{99m}Tc-rhAnnexin V-128 uptake at sites of active disease in SpA patients at presentation.

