6.1.1.3 Secondary endpoints

The secondary endpoints of Phase II and the related statistical analyses are:

- a) Endpoint: to determine the clinical utility of ^{99m}Tc -rhAnnexin V-128 SPECT/CT imaging in the identification of chronic osteoarthritic active sites of SpA compared with conventional imaging (MRI), in patients with disease affected sacro-iliac or lumbar spine joints.

Statistical analysis: for quantifying the radioactivity uptake after injection of ^{99m}Tc -rhAnnexin V-128, ROIs will be drawn manually on the earliest images, and the shapes and sizes (i.e. number of pixels) will be kept constant over all subsequent images. Correction for background counts will be performed using an appropriate background region by subtracting the mean counts per pixel in the background region from the mean counts per pixel in each ROI to yield net counts. For each ROI, the geometric mean of net counts, corrected for physical decay, of total anterior and posterior counts will be calculated. In order to compare SPECT/CT scans and MRI scans, diagnostic performances will be evaluated in terms of sensitivity (i.e. true positive rate), specificity (i.e. true negative rate), positive predictive value (i.e. proportion of positive values) and negative predictive value (i.e. proportion of negative values). This analysis will be performed for both region, sacro-iliac and lumbar spine joints. To do this, physical examinations will be necessary to define sites of pain in patients with clinical suspicion or confirmed diagnosis of SpA. When sites of pain will match with abnormalities on diagnostic images, this will be regard as true positive. Furthermore, for all the performed statistics, a two sided 95% C.I. will be computed

[figure not shown]
	MDL Modello	Area: 01 Documento: MDL 01.01 Revisione: 0 Data di revisione: 18/04/2013 Pagina: 30 di 85
	Statistical Analysis Plan	
ANNEXIN 03		

- b) Endpoint: to assess the presence of antibodies against rhAnnexin V-128 at baseline and post-treatment.

Statistical analysis: The determination of antibodies against rhAnnexin V-128 at baseline and post-treatment will be described as present or absent; these data, related to immunogenicity, will be described in contingency tables reporting frequencies and percentages.

- c) Endpoint: to determine the localization pattern and magnitude of focal uptake of ^{99m}Tc-rhAnnexin V-128 within the abdomen in patients with clinical suspicion or confirmed diagnosis of Spondyloarthritis (SpA).

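### Do the wrong glosses of PPV and NPV, and the shifting truth standard and target condition, call for a change to the plan?

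*Protocol*

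**What the plan says.** **Accuracy measures.** Protocol 10.9 (Secondary endpoints) names four measures for comparing SPECT/CT with MRI. Sensitivity and specificity are explained correctly, as the true positive and true negative rates. The other two are given as "positive predictive value (i.e., proportion of positive values) and negative predictive value (i.e., proportion of negative values". SAP 6.1.1.3(a) has the same words: "positive predictive value (i.e. proportion of positive values) and negative predictive value (i.e. proportion of negative values".

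**Truth standard.** The Statistics part of the protocol synopsis says sensitivity and specificity "will be evaluated based on the clinical follow-up information as the standard of truth for disease diagnosis". Protocol 10.9 instead uses painful sites found on physical examination: "When sites of pain will match with abnormalities on diagnostic images, this will be regarded as true positive". SAP 6.1.1.3(a) follows 10.9.

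**Target condition.** The opening text of protocol section 4 wants the tracer "to distinguish between active autoimmune arthritis versus osteoarthritis particular of the lumbosacral spine and SI joints". Protocol 4.2 expects that it "will be highly specific in imaging degenerative osteoarthritis particularly of the lumbosacral spine", and SAP 4.1.4 says the same: "will be highly specific in imaging degenerative osteoarthritis particularly of the lumbosacral spine and sacroiliac joints". The synopsis objective is utility "in the identification of chronic osteoarthritic active sites of SpA compared with conventional imaging", and protocol 4.1 and SAP 4.1.2 are close to that.

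**Status of the analysis.** SAP 6.1.1 opens by setting the efficacy endpoints aside because the study stopped early, and sends the efficacy data to listings and a descriptive abbreviated report. SAP 8 repeats this: the sponsor closed the study after 5 patients, and only listings and a short close-out report will be produced.

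**Listings.** The Imaging Results shell (Listing 16.2.6.1) has one Result column beside grades from the PI and two reviewers. The Disease Assessment shell (Listing 16.2.4.2/2) has MRI results as Positive or Negative, and clinical pain as Yes or No, for the lumbar spine and the sacro-iliac joints.

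**The concern.** A predictive value is conditional on the test result and needs a truth standard. The share of results that are positive is a different quantity and needs none. A programmer who coded the parentheses literally would report the wrong statistic under the right name.

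The other two points go deeper. If truth is a painful site on examination, the table measures agreement with pain and not diagnostic accuracy. If the target is osteoarthritis in one section and autoimmune arthritis as distinct from osteoarthritis in another, a positive scan at an osteoarthritic site is a success under one and a false positive under the other.

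For the output that remains, a reader of the listings might not know what Positive means for SPECT/CT or MRI, or whether it follows from the grades printed next to it.

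**Working it through.** The documents give no accuracy target or power figure, so there is none to reproduce. The check has four steps.

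**1. Size of the gloss error if it were applied.** Let p be the share of truth-positive regions and Se and Sp the sensitivity and specificity. As proportions of all regions, TP = p·Se, FP = (1 − p)(1 − Sp), FN = p(1 − Se), TN = (1 − p)·Sp. The standard definitions are PPV = TP/(TP + FP) and NPV = TN/(TN + FN). The literal glosses are TP + FP and TN + FN. The documents give no p, Se or Sp, so I assume Se = Sp = 0.8 and vary p:

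| p | PPV | literal gloss | NPV | literal gloss |
|---|---|---|---|---|
| 0.25 | 0.20/0.35 = 0.571 | 0.350 | 0.60/0.65 = 0.923 | 0.650 |
| 0.50 | 0.40/0.50 = 0.800 | 0.500 | 0.40/0.50 = 0.800 | 0.500 |
| 0.75 | 0.60/0.65 = 0.923 | 0.650 | 0.20/0.35 = 0.571 | 0.350 |

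The two glosses sum to 1 in every row. For a perfect scan (Se = Sp = 1) the literal PPV is p, where the true value is 1. The gloss is wrong, and by a wide margin.

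**2. Does any planned output use it?** SAP 6.1.1 is the parent section of 6.1.1.3, and its opening text sets the efficacy endpoints aside. SAP 8 says the same under changes from protocol. The number of planned sensitivity, specificity, PPV or NPV results is 0. The same holds for anything that depends on the truth standard or the target condition.

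**3. Would the comparison have been informative at this size?** SAP 6.1.1.3(a) analyses each region separately, so 5 patients give at most 5 SPECT/CT–MRI pairs per region at one time point. The smallest exact two-sided McNemar p is 2 × 0.5⁵ = 0.0625, above 0.05. Even 5 correct out of 5 has an exact 95% lower limit of 0.025^(1/5) = 0.478, so the interval is 47.8% to 100%. Dropping the analysis loses little, and repairing its definitions gains nothing here.

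**4. What remains in the listings.** If all 5 patients were imaged in both regions at 60 and 120 minutes, there are 5 × 2 × 2 = 20 SPECT/CT results and 5 × 2 = 10 MRI results. Abdomen, whole-body and spot results, which SAP 10.1 also lists, come on top. The 0 to 3 scale in protocol 10.9 has no cut-off for a positive scan, and the majority rule in SAP 6.1.1.2 returns a grade. That section and the abdominal endpoint in SAP 6.1.1.3(c) name the imaging result separately from the uptake grades, and SAP 11.4 does not include it among the derived variables. The natural reading is that Result is entered by a reader and not computed from the grades. The shell's sample row fits this: grades 0, 0 and 1 stand beside Positive, though their majority is 0. Those are dummy data and show no actual error.

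**The case for a change.** The best argument for acting concerns the listings. They are the only efficacy output left, SAP 6.1.1 says the data will be described in the report, and a footnote costs almost nothing. The MRI shell shows no grade, so a reader cannot apply a cut-off there. If no rule was set before the images were read, saying so would be honest disclosure.

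This part stands: a footnote on who assigned Positive or Negative, and by what rule, would be useful. It needs no change to the plan, because SAP 10 already tells the programmer to use footnotes to clear up ambiguities. Nor is it certain that a rule is absent. There is a redaction inside the grading text of SAP 6.1.1.2, a missing figure in 6.1.1.3(a), and neither the eCRF nor the DMC charter is available here. The MRI shell does give a number of inflammatory joints beside the result.

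On the truth standard, the conflict is partly under-specification. Physical examination is scheduled at screening and at Day 30, and section 10.9 does not say which one defines the painful sites, so clinical follow-up could include the Day 30 examination. Against that reading, the listing shell puts pain with the disease assessments, whose clinical scores are taken at screening. The conflict over the target condition is real and has no such reading.

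SAP 6.1.1.3(a) still describes the accuracy analysis in the future tense. A pointer back to 6.1.1 would add nothing, since 6.1.1 is its own parent section.

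**Conclusion.** No change follows. The PPV and NPV glosses are wrong, but the measures are named by their standard terms next to two correctly explained ones, and a statistician would compute them in the usual way. The truth standard is loosely stated and the target condition is contradictory. All three faults sit in an analysis the SAP has set aside, so they affect 0 planned results.

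The undefined Positive or Negative label touches about 20 SPECT/CT and 10 MRI entries in the two regions of interest. This is a missing detail that analysts can supply under the existing footnote instruction. The SPECT/CT listing stays readable because every reader's grade is shown.

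This rests on SAP 6.1.1 and SAP 8 being followed as written. If the accuracy analysis were revived, or its wording carried into another study, the predictive values, the truth standard and the target condition would have to be corrected and reconciled first.
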